- 1) **Date:** 12/18/23
- 2) **Study Title:** Supplementation with a Next Generation Synbiotic in Individuals with Overweight or Obesity: A Triple-Blinded Randomized Controlled Trial
- 3) **Principal Investigator (must be a TCU faculty or staff):** [name]
- 4) **College/School:** Texas Christian University
- 5) **Other Investigators:** List all faculty, staff, and students conducting the study. For those not affiliated with TCU, please provide their names and institution.
[name], [name], [name], [name], [name], [name], [name], [name], [name], [name], and [name]
- 6) **If you have internal or external funding for this project –**
Funding Agency: The supplement company Pendulum will provide the product (probiotic and placebo with a market value of \$50,400). The Dean's Opportunity Fund will provide \$49,512 for blood analyses, blood and stool sample tubes, and stool sample whole genome sequencing. [name] will provide part of her start up funds (\$6,000) for participants compensation. **Project #: IRB#2023-345** **Date for Funding:** November 2023
- 7) **If you intend to seek/are seeking internal/external funding for this project –**
Funding Agency: TCU Graduate SERC Grant
Amount Requested From Funding Agency: \$2,000
Due Date for Funding Proposal: October 23rd, 2023
- 8) **Purpose: Describe the objectives and hypotheses of the study and what you expect to learn or demonstrate:** Our proposed triple-blinded, placebo controlled, randomized clinical trial is divided into two stages.
The first stage will consist of exploring the effect of next generation synbiotic supplementation for 12 weeks on body composition, insulin sensitivity, gut microbiota composition and diversity, depression, anxiety, and food cravings in 60 individuals with overweight or obesity who have no diagnosis of diabetes mellitus (DM). For this first stage, we hypothesize that this next generation synbiotic will decrease adiposity, overall body weight, anxiety, depression, and food cravings and increase insulin sensitivity, and gut microbiota diversity. We also hypothesize that the levels of bacterial species in the symbiotic will increase in the gut microbiome.

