visit, depending on the order they enrolled, participants will receive the 3 bottles containing the assigned code. Participants will also be provided with two stool sample collection kits, a 3-day diet record form, a 3-day prescription of antibiotics (500 mg of generic Vancomycin every 8h), date for second appointment, and a start date for the antibiotic regimen. The 3-day antibiotic treatment provided prior to beginning the 12-week synbiotic intervention is given with the intention to increase the number of available bacterial niches (bacterial homes/space) and thus increase the engraftment of the newly ingested bacteria. Although participants will be asked to pay the cost of the generic antibiotic treatment initially (which should have an estimated cost of \$20-25), we will offset the cost of the antibiotic by providing the participants with a \$50 Amazon gift card in their second appointment, so they will not be responsible for any costs to participate in this study. This initial gift card is in addition to their \$100 Amazon gift card provided at the end of the study in appreciation for having taken part in this project. Their insurance will not be charged for any study-related testing; however, they are welcome to (but don't have to) use their insurance to buy the antibiotic. During this first visit, participants will have their 1) first 12h fasted blood collection and will be instructed to 2) fill out a 3 day food log before each stool sample collection, 3) collect a stool sample before the start of the antibiotic regimen, 4) collect a stool sample within 12-48 hours after the last dose of the antibiotic regimen, 5) bring both stool samples and diet records with them to the second appointment and, 6) fast 12 hours prior to the second appointment (refrain from the consumption of all food and liquids, except water). The first appointment is expected to take no greater than 45 minutes.

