For the second visit, participants will meet researchers at the Rickel building. This appointment is expected to take approximately 45 minutes and includes the completion of a DEXA scan, an air displacement plethysmography test (via BOD POD), body weight measurement, the Beck Anxiety and Depression Inventories, the RED-9 questionnaire, and a blood draw. Participants will turn in their first (before antibiotic prescription initiation) and second (after antibiotic prescription completion) stool samples and food logs to researchers. The blood draw will consist on 2 serum separation tubes (10 mL each), 1 EDTA tube (3 mL), and 1 Zymo tube (3 mL). The time to complete each test is approximately as follows: 10 minutes for the blood draw, 10 minutes for the anxiety and depression survey, 20 minutes for the DEXA scan, and 5 minutes for an air displacement plethysmography test. Air displacement plethysmography tests via the BOD POD will be used to measure body fat percentage. Participants will be asked to wear minimal clothes and no shoes for the air displacement plethysmography test. The DEXA scans will be used to measure fat mass, visceral fat, lean mass, and bone mineral density. The DEXA scan uses a two-sided low emission X-ray to quantify lean body mass, fat mass, and bone density. To conduct the test, participants will be asked to void their bladder, remove all metal objects (piercings, rings, etc.) and shoes, and will lay supine on a padded table for approximately 6 minutes while the scanner moves down the length of the participant's body. Measurements will be conducted by a General Electric Certified DEXA Operator ([name] or [name]). Blood samples will be collected using sterile techniques and only by qualified investigators ([name] or [name]). Blood samples will be used to measure fasting glucose, fasting insulin, and HbA1C. Blood will be sampled using venipuncture. The venipuncture samples will be collected using a traditional blood draw needle to extract blood from a vein in the antecubital region of the arm. Two 10 mL vials of blood will be collected, centrifuged to separate the serum. One of those tubes will be stored in a -80°C freezer in the Exercise Physiology Laboratory (Rickel 259) whereas the other will be transported to BioReference for fasting glucose and insulin analysis. The 3 mL for EDTA analysis will also be transported to BioReference for HbA1C analysis. The Zymo collection tube (3 mL) will be stored at the Rickel 259 building. All blood collection vials and plasma/serum containers will be

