
labeled using participant numbers (deidentified) for participant privacy. The leftover blood samples will be stored in the laboratory for 10 years from date of collection at which point they will be discarded as biohazard waste. Participants agree to allow their deidentified samples to be used for future research by signing the informed consent. These procedures have been approved by the TCU Institutional Biosafety Committee (IBC Protocol). At the end of the second appointment, participants will be provided with the 12 weeks of the probiotic+prebiotic supplement. Each person will receive 3 bottles (one per month) with the three of them having the same ID, this same ID will be used to identify all questionnaires and samples obtained from that person. This ID will also be different between each participant. Participants will also be instructed to 1) record everything they eat for 72 hours before stool sample collection, 2) collect a stool sample within 24 hours of finishing the last dose of the intervention, 3) bring the stool sample, diet record, and remnant of their supplement or placebo with them to the third appointment, and 4) fast 12 hours prior to the third appointment (refrain from the consumption of all food and liquids, except water).

The third and final appointment is expected to also take approximately 45 minutes and will include a replication of all tests conducted in the second appointment (completion of a DEXA scan, an air displacement plethysmography test [via BOD POD], body weight measurement, the Beck Anxiety and Depression Inventories, the RED-9 questionnaire, and a blood draw [consisting on 2 serum separation tubes of 10 mL each, 1 EDTA tube of 3.5 mL, and 1 Zymo tube of 3mL]). Participants will turn in their third and final stool sample, as well as the remnant of their supplements or placebo for analysis of adherence and compliance. Participants will receive a \$100 Amazon gift card at the end of the study in compensation for their time. After all stool samples have been collected, they will be sent in the same batch to the Alkek Center for Metagenomics and Microbiome Research (CMMR) at Baylor College of Medicine in Houston for posterior whole genome sequencing analysis.

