If participants withdraw from their study the data collected up to that point will remain available for research purposes with the intention to use intent to treat analysis. Blood and stool samples will be stored in [name] lab located within the Rickel building room 259. For the first stage of the project, blood samples will be analyzed at [name] lab room 259. Once the Nutritional Sciences Department laboratory has been finalized, samples will be transferred to the Nutritional Sciences Department and further storage and analyses could take place here (BASS, room 1203). If enough funds become available to perform the second stage of the study, blood and stool samples (which will be identified by fabricated ID) will be sent to Baylor College of Medicine and to Metabolon for posterior 16S rRNA/WMS and mass spectrometry analyses, respectively. For statistical analysis of the first stage, two sample T-tests will be used to compare within (pre- versus post- values on each group) and between-group (placebo versus probiotic) differences in body composition, adherence, metabolic, dietary, and psychological variables. SPSS will be used for statistical analysis. A p value <0.05 will be considered as statistically significant. Dietetic variables collected via the NCI Automated Self-Administered 24-hour Dietary Assessment Tool including protein, carbohydrate, fat, and fiber will be controlled statistically in the case that significant intra-individual or between-group differences are observed.

20) Check List for the Items That Need to be Submitted: Please submit protocol and consent documents separately in MS word, supplemental documents (interview guides, surveys, recruitment materials etc. can be submitted as separate pdfs) before submitting the materials electronically to the IRB. To prevent any delay in the approval of your protocol, use the most recent template for the protocol, consent document, and HIPAA form by downloading them from <https://research.tcu.edu/research-compliance/irb/irb-forms-templates/> each time you prepare your materials.

a. Protocol	X
b. Consent document	X
c. Protecting Human Research Participants Training complete for each investigator	X
d. Recruitment flyers, letters, ads, etc.	X
e. Questionnaires or other documents utilized in screening and data collection	X

Principal Investigator Assurance

21) By signing below, I certify to the following:

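### Section 19 tests pre-versus-post change within each arm without saying which of two pre-product samples is 'pre', and states no test for the stage-1 stool hypotheses

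*Combined protocol and SAP*

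**What the plan says.** **Stool (section 14).** There are three samples per person. At the first visit participants are told to "collect a stool sample before the start of the antibiotic regimen" and then to "collect a stool sample within 12-48 hours after the last dose of the antibiotic regimen". Both are handed in at visit 2 as the "first (before antibiotic prescription initiation) and second (after antibiotic prescription completion) stool samples". After the 12-week product period they "collect a stool sample within 24 hours of finishing the last dose of the intervention". Neither early sample is called baseline.

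**Blood (section 14).** Visit 1 includes the "first 12h fasted blood collection". A second fasting draw follows at visit 2, after the antibiotic and before the product. Glucose, insulin and HbA1c are described under visit 2, and visit 3 is described as repeating the visit 2 tests.

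**Antibiotic.** "The 3-day antibiotic treatment provided prior to beginning the 12-week synbiotic intervention" is part of the procedure for every participant, whichever product they are allocated. Section 15 describes the microbiota changes after such a short course as minimal, passing and reversible, and gives no figure.

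**Hypotheses (section 8).** The product is expected to "increase insulin sensitivity, and gut microbiota diversity". The species it contains are also expected to rise in the gut.

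**Analysis (section 19).** For stage 1, "two sample T-tests will be used to compare within (pre- versus post- values on each group) and between-group (placebo versus probiotic) differences". The variables listed are body composition, adherence, metabolic, dietary and psychological measures. Microbiota and diversity are not among them. The threshold is p<0.05. The only other stage-1 provision is a conditional adjustment for dietary variables.

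**The concern.** There are two gaps, and they compound each other.

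First, 'pre' has two possible meanings for blood, and would have two for stool if stool were analysed the same way. The candidates lie on either side of an antibiotic that is given precisely to disturb the gut community. Left unnamed, the baseline can be chosen after the data are seen.

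Second, the stage-1 stool hypotheses have no stated test. The section 19 t-tests are the only stage-1 tests on offer, so an analyst may well reach for them. If diversity were tested within arm from the post-antibiotic stool, any antibiotic-induced drop that recovers by week 12 would move both arms in the direction that section 8 predicts, even with an inert product. A significant rise in the synbiotic arm could then be reported as support for the hypothesis.

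**Working it through.** The plan states no power, effect size or SD for this outcome, so there is no figure to reproduce. What follows is an illustration.

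**Inputs**
- 60 participants (section 11). The allocation ratio is not stated; n = 30 per arm is assumed, with no dropout.
- Alpha 0.05 (section 19), two-sided assumed.
- Product effect: none.
- Antibiotic drop at stool 2, fully recovered at stool 3: d = 0.2, 0.3, 0.5 or 0.8 SD. Assumed; the documents give no figure.
- Correlation between a person's samples: r = 0.5, range 0.3-0.7. Assumed.

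**Paired within-arm test, stool 3 minus stool 2.** The SD of change is √(2(1−r)), which is 1 at r = 0.5. The noncentrality is d√n / √(2(1−r)), with 29 df and critical value 2.045. For d = 0.5 it is 0.5 × √30 = 2.74, and the noncentral t gives a rejection probability of 0.754.

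**Two-sample test as written, applied to the same correlated data.** The test assumes a standard error of √(2/30) = 0.258 and needs a mean difference of about 2.002 × 0.258 = 0.517 SD. The true standard error at r = 0.5 is √(2 × 0.5/30) = 0.183. For d = 0.5 the normal approximation is P(Z > (0.517 − 0.5)/0.183) = P(Z > 0.09) ≈ 0.46; simulation gives 0.47.

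| Recovery d (SD) | Paired, r = 0.5 | Paired, r = 0.3 to 0.7 | Two-sample as written, r = 0.5 |
|---|---|---|---|
| 0.2 | 19% | 15-28% | about 5% |
| 0.3 | 36% | 27-54% | about 13% |
| 0.5 | 75% | 61-93% | about 47% |
| 0.8 | 99% | 95-100% | about 93% |

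The two-sample form is also wrong for paired values. With no shift at all it rejects only about 0.6% of the time at r = 0.5, so the 5% at d = 0.2 SD is nominal by coincidence.

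**Comparators** (20,000 simulated trials, r = 0.5, d = 0 to 0.8 SD)
- Pre-antibiotic stool as 'pre', paired within arm: rejection 0.049-0.052. No inflation, provided recovery is complete.
- Change from the post-antibiotic stool compared between arms: rejection 0.048-0.051. No inflation.
- Exactly one arm significant in the paired test, with no true difference between arms: 30% at d = 0.2 and 37% at d = 0.5. Contrasting the two arms' within-arm p-values is therefore unsafe even when recovery is the same in both.

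**The case against.** **A reader might infer that section 19 plans a within-arm test of stool diversity.** It does not say so. The variable list that follows the t-test statement leaves out microbiota, and the only explicit pre/post microbiome comparison with diversity measures is for stage-2 blood (section 14). The inflation is what would follow if the stage-1 test were carried over to diversity. What the text does show is that no stage-1 stool test is stated.

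**A reader might infer that the trial's treatment comparison is biased.** It is not. Both arms take the antibiotic, randomisation balances recovery, and section 19 also plans between-group tests. Nor does the plan say how within-arm results would be interpreted.

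**A reader might take the paired percentages as the plan's error rate.** The plan says two-sample, which gives lower figures in the illustration. Section 15 also calls the antibiotic changes minimal, so the small end of the range is plausible, and there the literal test is close to nominal.

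**A reader might think that either stool misleads equally.** If recovery is complete by week 12, the pre-antibiotic stool gives no inflation. It mixes antibiotic and product effects only to the extent that recovery is incomplete.

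**On blood,** visit 2 is the natural baseline because visit 3 repeats its tests. That is a reasonable inference, but section 19 does not state it. Body composition and the questionnaires are scheduled only at visits 2 and 3. Body weight is also measured at visit 1 for eligibility, but the same inference points to visit 2.

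What stands is the undefined 'pre', the missing stool analysis, and within-arm tests held to the same p<0.05 as the randomised comparison.

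**Conclusion.** The point holds in a limited form. Two pre-product stools and two pre-product blood draws exist, section 19 does not say which is 'pre', and the stage-1 hypotheses on diversity and species levels have no stated test. If the within-arm test were used for diversity from the post-antibiotic stool, recovery alone could pass for a product effect. The false-positive rate would run from 19% to 99% with a paired test and from about 5% to 93% with the two-sample test as written, for recoveries of 0.2 to 0.8 SD. These figures rest on assumed values: the drop, complete recovery, correlation 0.5 and 30 per arm. They show direction and sensitivity; they do not estimate this trial's error rate. The between-arm comparison is unaffected. The plan should be corrected before unblinding, but the design itself is sound on this point.

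**What to change.** Amend section 19 as follows.

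1. Add the stage-1 stool outcomes (diversity and the levels of the product's species) to the analysis.
2. Base efficacy for stool and metabolic outcomes on a between-arm comparison at visit 3 adjusted for baseline (ANCOVA), in place of the within-arm tests.
3. For stool, adjust for the post-antibiotic value, and optionally also for the pre-antibiotic value.
4. For glucose, insulin and HbA1c, adjust for the visit 2 value, since visit 3 repeats the visit 2 tests.
5. Report within-arm changes, including the change between the two early stools, as description only, without significance claims.

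The cost is one paragraph and one or two degrees of freedom: with 60 analysed, 58 for the between-arm t-test becomes 57 with one covariate or 56 with two. All the samples needed are already scheduled.

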In the first visit, participants will come for 45 minutes to the Rickel Department where they will receive a complete explanation of the protocol and will process to sign the "Informed Consent to Participate in Research and Authorization to Collect, Use, and Share their Health Information" if agreeing to participate. Participants' height and weight will be measured to ensure they meet BMI inclusion criteria. Height will be measured using a standard stadiometer and weight will be measured using a standard calibrated digital scale. Their race will be asked to help in data interpretation. Height, weight, race and other information relevant to antibiotic prescription such as date of birth, allergies to medications, and preferred pharmacy will be collected at this time point using our document titled "checklist 2". All symbiotic and placebo bottles will be entirely similar with exemption of individual codes that will vary every 3 bottles. This is because each participant will be provided at the beginning of the study with 3 bottles (with similar code) to ensure enough supply for the 12-week supplement intervention. The company Pendulum will perform an *a priori* randomization of the entire study by using blocked randomization with randomly selected blocked sizes with the intention to reduce bias and ensure balance between groups. This randomization will be added into an Excel document in which they will specify the order of the participant in column 1 (example: Participant 001, Participant 002), the code of the bottles in column 2, and the interpretation of the code (placebo vs probiotic) in column 3. A researcher, independent from this study ([name]), will save in different protected locations (Box, secured laptop, protected USB) the randomization document. [name] will share with [name] an Excel document containing column 1 and column 2 of the provided document (the order of participant and the code of the bottles, without the interpretation of each code). [name] will use the supplement code as the participants' IDs and study data will be added to this Excel document. Both documents, from, [name] and from [name], will be merged at the end of the study, once data has been analyzed to figure out the intervention group to which each participant belonged. During the first

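### The product has two conflicting hand-out times, one of which allows a start before the visit 2 baseline; separately, no antibiotic intake or dose dates are described as recorded

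*Combined protocol and SAP*

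**What the plan says.** All of this is in section 14 (Study Procedures, Stage 1) of the combined protocol and SAP unless noted.

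**Product hand-out.** The first-visit text explains the bottle coding and says "each participant will be provided at the beginning of the study with 3 bottles", enough for the 12 weeks. It then says that during this visit, in order of enrolment, "participants will receive the 3 bottles containing the assigned code". The second-visit text closes by providing the 12-week supply at the end of that appointment, again three bottles sharing one ID.

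**Antibiotic.** At visit 1 participants get a prescription for three days of vancomycin, 500 mg every 8 h, to precede the synbiotic. They leave with a "date for second appointment, and a start date for the antibiotic regimen". They obtain the drug themselves: "participants will be asked to pay the cost of the generic antibiotic treatment initially", offset by a gift card at visit 2. They are told to "fill out a 3 day food log before each stool sample collection", to take one stool before the antibiotic, to "collect a stool sample within 12-48 hours after the last dose of the antibiotic regimen", and to "bring both stool samples and diet records with them to the second appointment".

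**Baseline.** The second visit "includes the completion of a DEXA scan, an air displacement plethysmography test (via BOD POD), body weight measurement", along with the Beck inventories, RED-9 and a blood draw.

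**Adherence and analysis.** Leftover supplement or placebo is returned at visit 3 to assess adherence; the antibiotic is not mentioned there. Section 19 compares pre with post values within groups and compares the two groups, with intention-to-treat handling of withdrawals.

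**The concern.** The two hand-out statements cannot both describe one supply, and both are current instructions to staff. The visit 1 version is the one that matters. It puts product in the participant's home before the only pre-intervention DEXA, BOD POD, Beck and RED-9 values are taken. If someone starts early, those values are no longer pre-product and there is no earlier measurement to use instead. Weight and fasting blood are also taken at visit 1, so they are less exposed. Stool 2, the one post-antibiotic sample meant to precede product, could be affected in the same way. An active product would shift the baseline only in the synbiotic arm, which would tend to shrink that arm's pre-to-post change.

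The antibiotic record is a separate matter. The protocol makes the product's effect after a short antibiotic course the main purpose of the sequencing, and it hypothesizes that the course aids colonization. Section 15 describes the microbiota changes from short courses as small and reversible, so doses taken and the gap to the first product dose bear on how an engraftment result is read. If engraftment is null, the team would want to tell a product that failed to engraft from missed antibiotic doses or a long gap.

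**Working it through.** The plan states no figure for this point, so there is none to reproduce. The check compares the texts and then does simple interval arithmetic.

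**1. Is it one supply?** The first-visit text has three bottles with one code, covering 12 weeks. The second-visit text has three bottles with one ID, covering 12 weeks. Quantity, coding and duration match, so this is one supply with two delivery times.

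**2. What is recorded about the antibiotic and first product dose?**
- Given out at visit 1: a planned antibiotic start date. This is not an actual date.
- Checklist 2: prescribing information such as allergies and pharmacy, collected before any dose is taken.
- Handed in at visit 2: two stools and food logs.
- Handed in at visit 3: a third stool, and leftover supplement or placebo.
- Not described anywhere visible: antibiotic doses taken, time of the last antibiotic dose, date of the first product dose.

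**3. Antibiotic course, from the prescription.**
- Doses: 3 days × 24/8 = 9.
- First to last dose: 8 intervals × 8 h = 64 h.
- Stool 2 after the first dose: 64 + 12 = 76 h to 64 + 48 = 112 h.

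**4. Gap in which product could be started without breaking the stated order.** This runs from the last antibiotic dose to visit 2. Visit 2 cannot precede stool 2, which is brought to it, so the gap is at least 12 h if the instructions are followed. The protocol sets no upper limit. Assuming visit 2 is held 12 to 48 h after the last dose:
- Lower: 12/24 = 0.5 day; 0.5/84 = 0.6%.
- Upper: 48/24 = 2 days; 2/84 = 2.4%.
- Each further day before visit 2 adds 1/84 = 1.2%.

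The denominator is 12 × 7 = 84 days. The Figure 1 caption says four months instead; a longer course would make these shares smaller.

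**5. Time bottles would sit at home under the visit 1 rule.** This is at least 64 + 12 = 76 h (3.2 days) if the antibiotic starts at once. It is 72 + 64 + 12 = 148 h (6.2 days) if the food log before stool 1 takes a full 72 h. This is holding time, not exposure.

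**The case against.** The strongest reply is that the intended sequence is clear. The antibiotic is stated to precede the 12-week product period, none of the numbered visit 1 instructions tells participants to take product, and the product-period instructions come at the end of visit 2. On that reading the code is assigned at visit 1, the bottles are handed over at visit 2, and the first-visit wording is merely loose. This may well be the intent, but the text says participants receive the bottles, and staff following it would hand them over.

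The reply does dispose of a stronger reading. A reader might take the 6.2 days of holding time as product exposure and infer that about 7% of the course (6.2/84) could precede baseline. That requires starting product at visit 1 and taking it through the antibiotic course, contrary to the stated order. It also reads the first food log as a full 72 h, wording that appears only for the final stool. The figure should not be used.

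On the antibiotic, three counter-arguments have force. The stools before and after the course, sequenced by shotgun methods, show the microbial response directly. No analysis in section 19 depends on a dose count. The data-collection forms were submitted separately (section 20) and may capture dates. These make the record a useful addition rather than a defect in the comparison. They do not supply doses taken or the gap to first product, which are harder to obtain reliably by recall later. Nor could unseen forms remove the contradiction in the protocol text.

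**Conclusion.** The hand-out conflict is real and should be corrected. The exposure it leaves open is small if visit 2 promptly follows the antibiotic: about 0.5 to 2 days, or 0.6% to 2.4% of 84 days. It grows with any booking delay. The number of participants who would start early cannot be estimated from the documents, and no loss of power is claimed.

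The missing antibiotic record is a separate and lesser point. A reader might infer that it biases the treatment comparison. It does not: every participant is prescribed the same course whatever the allocation, and allocation is randomized and blinded. What it limits is the explanation of an engraftment result, particularly a null one. This part rests on the visible text alone; the design figure and the data forms could not be checked.

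**What to change.** **Hand-out.** Correct the first-visit text in section 14 so that the code is assigned at visit 1, since it serves as the participant ID, while staff keep the bottles. Dispense product only once the visit 2 measures are complete, as the second-visit text already has it.

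**Antibiotic and dates (low-cost addition, unless the unseen forms already cover it).** Ask participants to bring the antibiotic container to visit 2 and count the remaining doses. Record the date and time of the last antibiotic dose, stool 2 and the first product dose. Keep everyone in the intention-to-treat comparison, and use these data only descriptively, alongside the paired stools, to interpret engraftment.

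**Cost.** One text correction, about a minute and a few data fields per participant, and staff storage of coded bottles between visits 1 and 2.
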